### 10.3.2 Adverse Events of Special Interest

[REDACTED] is considered an adverse event of specifical interest (AESI) in this trial. The AESI is collected from adverse event report and from [REDACTED] procedure.

[REDACTED]  
[REDACTED]  
[REDACTED]  
[REDACTED]  
[REDACTED]

[REDACTED] procedure data will be evaluated for both treatment periods (start from first dose at HZNP-HZN-825-301 and at HZNP-HZN-825-302 to the end of HZNP-HZN-825-302).

Symptoms reported on the [REDACTED] procedure may not be reported as adverse events, and will not be reconciled as such. Any spontaneously reported signs or symptoms possibly associated with [REDACTED] will be captured as AEs. These will be identified based on the flag within the dataset and/or programmatically using the standard MedDRA query (SMQ) search criteria as needed.

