#### **9.5.3.1.1.4 Adverse Events of Special Interest**

An AESI is an AE (serious or non-serious) of scientific and medical concern specific to the Sponsor's product or program, for which ongoing monitoring and rapid communication by the Investigator to the Sponsor may be appropriate. Such events may require further investigation in order to characterize and understand them. AESIs may be added or removed during a trial by protocol amendment.

The following AESI is identified for this trial:

If any symptoms occur during the assessment in combination with the blood pressure reductions noted above, they are considered as part of the [REDACTED] event and will not be recorded separately as individual AEs.

If symptoms are reported by the subject throughout the assessment, without the blood pressure reductions noted above, then the symptoms will be recorded separately as AEs and [REDACTED] will not be recorded.

Signs and symptoms associated with [REDACTED] reported outside of the assessment will be captured as part of spontaneously reported AEs at each visit.

Depending on the timing, nature and severity of these spontaneous AEs, additional investigations will be conducted at the next scheduled visit or at an unscheduled visit, as clinically indicated per the Investigator's judgment. Whenever possible, the following data should be collected: concomitant medications, and blood pressure and heart rate measurements in supine and standing positions. Depending on the severity, plasma glucose level and ECG should be obtained per Investigator's clinical judgment.

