Events for which the investigator did not record relationship to trial drug will be considered related to trial drug for summary purposes. However, by-subject data listings will show the relationship as missing. No imputation will be done in case of missing study treatment relationship for non-treatment emergent AEs.

The severity grade of events for which the investigator did not record severity will be categorized as “missing” for tabular summaries and data listings. The missing category will be listed last in summary presentation.

Treatment-emergent AEs will be summarized based on the Safety Analysis Set.

Summaries of the following types will be presented:

The number and percentage of subjects who experienced at least 1 TEAE will be provided and summarized by SOC, PT, and treatment group.

The following AEs summaries will be provided by SOC, PT, and treatment group. AE summaries followed by an asterisk(\*) will include the number of events and the corresponding incidence of events per PYE.:

- All TEAEs by maximum severity
- All treatment-emergent SAEs\*
- All treatment-related TEAEs\*
- All treatment-related TEAEs by maximum severity
- All treatment-related treatment-emergent SAEs
- All TEAEs meeting CRISS criteria
- All TEAEs leading to permanent withdrawal of any trial drug
- All TEAEs leading to death (ie, outcome of death)
- All follow-up adverse events
- All serious follow-up adverse events
- Subject incidence of AESIs: [REDACTED]

A brief, high-level summary of AEs described above will be provided by treatment group for the study treatment period and by the number and percentage of subjects who experienced the above AEs. All deaths observed in the trial will also be included in this summary. For the overall summary, the category of “TEAEs by maximum severity” described above will be replaced by AEs with severity > Grade 3.

The frequency of TEAEs occurring in > 5% of subjects in any treatment group will be summarized by treatment, primary SOC, and preferred term. A similar summary will be created for serious TEAEs occurring in > 3% of subjects in any treatment group by primary SOC and preferred term.

An adverse event plot will be created with AE incidences and risk differences (with corresponding exact 95% confidence interval) plotted together for the adverse events occurring in >5% of subjects in any treatment group. A similar plot will be created for SAEs occurring in > 3% of subjects in any treatment group.

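### SAP 10.3.2 waives reconciliation of AESI-procedure symptoms that the protocol requires as AEs, so individual symptom TEAEs can be undercounted

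*SAP*

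**What the plan says.** Protocol Section 9.5.3.1.1.4 names one AESI (its name and blood pressure criteria are redacted) and sets recording rules for symptoms around the assessment that detects it.

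- With the blood pressure criteria met: "If any symptoms occur during the assessment in combination with the blood pressure reductions noted above, they are considered as part of the" AESI "event and will not be recorded separately as individual AEs".
- With the criteria not met: "then the symptoms will be recorded separately as AEs and [REDACTED] will not be recorded".
- Signs and symptoms outside the assessment are captured as spontaneously reported AEs.

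SAP Section 10.3.2 says of symptoms reported on the procedure that they "may not be reported as adverse events, and will not be reconciled as such". The visible text attaches no condition on the blood pressure result. The same section says "The AESI is collected from adverse event report and from" the procedure, that "procedure data will be evaluated for both treatment periods", and that spontaneously reported symptoms are captured as AEs and found by a dataset flag or an SMQ search. SAP Section 10.3.1 lists "Subject incidence of AESIs" among the AE summaries, next to the TEAE tables by SOC and PT.

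**The concern.** The SAP sentence treats all procedure symptoms alike, whereas the protocol makes an AE record mandatory for one group of them: symptoms without the blood pressure reduction. Those symptoms are not part of the AESI, and they are not spontaneous reports from outside the assessment. Nothing else in the visible SAP section picks them up, so whether they reach the TEAE tables depends on site entry alone.

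Incidence of TEAEs is a stated safety endpoint, and AEs are named in the primary safety objective. A symptom could be present in the trial's own procedure data and still be missing from every TEAE summary. The count would then depend partly on how each site handled the procedure page.

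**Working it through.** The plan states no figure to reproduce, and no rate, count or sample size bears on this point. The check is to set the two sections side by side.

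| Symptom | Protocol 9.5.3.1.1.4 | SAP 10.3.2, visible text | Agreement |
|---|---|---|---|
| During the procedure, with the reduction | Part of the AESI; no separate AE | May lack an AE record; not reconciled | Yes |
| During the procedure, without the reduction | Separate AE required; AESI not recorded | May lack an AE record; not reconciled | No |
| Outside the procedure | Spontaneously reported AE | Captured as AE; flag or SMQ | Yes |

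The second row fails under either reading of the SAP's wording. If it forbids an AE record, it contradicts the protocol. If it only says that a record might be absent, it foresees missing entries and declines to look for them.

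The count at risk follows from the same row. By the protocol's rule these symptoms are not the AESI, so what can be lost is the individual symptom TEAE.

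The size can be written only as a formula. With p the true proportion of subjects with a given symptom in this group and m the fraction of those subjects with no AE entry, the reported proportion is p × (1 − m). The documents give neither p nor m. Purely to show the mechanism, assume p = 6% in the treatment group with the highest rate:

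- m = 10%: 6% × 0.9 = 5.4%
- m = 50%: 6% × 0.5 = 3.0%
- The symptom leaves the SAP's display of TEAEs above 5% once m reaches 1 − 5/6, about 17%.

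These inputs are arbitrary and estimate nothing about this trial. The symptom would still appear in the SOC and PT table of all TEAEs, which has no threshold, but with too low a count.

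**The case against.** Several points on the other side are sound.

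- **AESI incidence.** A reader might infer that the AESI itself is undercounted. The documents do not support that. Symptoms without the reduction are by definition not the AESI, and the SAP takes the AESI from both AE reports and the procedure and says the procedure data will be evaluated. The flag and SMQ search are described for spontaneous symptoms; they are not stated as the only route to the AESI. The five redacted lines could hold the rule for combining the two sources.
- **Direction of error.** A reader might also infer that the error can only lower counts. The protocol bars two entries as well: a separate AE for symptoms with the reduction, and an AESI record for symptoms without it. If sites make those entries wrongly, the lack of reconciliation leaves an overcount. Only for omitted entries does the waiver work in one direction.
- **Sites follow the protocol.** The SAP does not excuse a site from recording an AE, so an undercount needs a site omission first. Protocol Section 13 calls for checks for omissions and for site queries, and Section 12 has monitors verify completeness. This lowers the likelihood of a shortfall, but general cleaning does not cancel an explicit decision against this particular cross-check.
- **Redaction and version.** The redacted SAP lines could contain a qualifier, although the sentence after them is unconditional as printed. The SAP is based on protocol Version 2.2, which is not supplied. The table of changes from Version 2.0 to 3.0 lists none to Section 9.5.3.1.1.4, so a version gap is not an evident explanation.
- **Consequence.** Safety is summarized descriptively in an open-label, single-arm trial, so no test depends on these counts.

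**Conclusion.** The two sections conflict for one defined group: procedure symptoms without the blood pressure reduction. The protocol requires an AE record; the SAP neither relies on one nor checks for it. Individual symptom TEAEs can therefore be undercounted wherever a site omits the entry. This is a possibility that the plan leaves unchecked, and no undercount has been demonstrated.

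The size cannot be derived from the documents. The conclusion assumes that at least some sites omit entries and that the redacted lines do not restrict the SAP sentence. Confidence is moderate for the second reason. The point is worth correcting because it touches a stated safety endpoint and the data needed are already collected.

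**What to change.** Reconcile the two sections. In SAP Section 10.3.2, limit the sentence to symptoms accompanied by the blood pressure reduction, where it already agrees with the protocol. Add that procedure symptoms without the reduction are checked against the AE data.

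Before database lock, produce one listing of procedures in this extension trial with at least one symptom, no qualifying reduction and no matching AE record, and send site queries on each line.

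The cost is one extra listing and some queries. Symptom TEAE rates may become slightly less favourable. No clinical rule changes.

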### 10.3.3 Clinical Laboratory Evaluations

#### 10.3.3.1 Summaries of Laboratory Results

Laboratory data collected during the trial will be analyzed and summarized using both quantitative and qualitative methods. Summaries of laboratory data will be provided for the Safety Analysis Set. Laboratory parameters to be summarized are listed in [Table 5](#).

**Table 5 Lab Parameters**

Chemistry	Hematology	Lipids and coagulation	Urinalysis
Total protein, albumin, sodium, phosphate, potassium, calcium, chloride, bicarbonate, blood urea nitrogen, creatinine, creatine kinase, uric acid, glucose, lactate dehydrogenase; liver function tests (alanine aminotransferase, aspartate aminotransferase, gamma glutamyltransferase, alkaline phosphatase, total bile acid, total bilirubin, conjugated and unconjugated bilirubin, if applicable;	Hemoglobin, hematocrit, Red blood cells, mean corpuscular volume, mean corpuscular hemoglobin, mean corpuscular hemoglobin concentration, red blood cell distribution width, reticulocyte count White blood cells count and differential (neutrophils, eosinophils, basophils, monocytes, lymphocytes), platelets, high sensitivity C-reactive Protein (hsCRP) and erythrocyte sedimentation rate (ESR)	Lipids: total cholesterol, high-density lipoprotein cholesterol, low-density lipoprotein cholesterol and triglycerides  Coagulation: prothrombin time, partial thromboplastin time, international normalized ratio and fibrinogen	Ketone, Specific Gravity, Urine Glucose, Urine Protein, Urobilinogen, and pH  Urinalysis also reports blood

Laboratory results collected in conventional units will be converted to International System of Units (SI) for all summaries and listings. Clinical laboratory test results (Hematology, Chemistry, Lipids and Coagulation, and Urinalysis) and their changes from baseline will be summarized by visit and treatment group using descriptive statistics.

For hematology, chemistry, and lipids and coagulation, results will be categorized as low, normal, or high based on their normal ranges. If toxicity grading is applicable to the laboratory result, toxicity grades will also be evaluated and assigned to the result. If available, shift tables using categories of toxicity grade comparing laboratory test results from baseline to each visit will be presented with percentages based on subjects with a non-missing value at

baseline and post-baseline visit. If toxicity grade is not available, then categories of low, normal, and high will be used for the analogous presentation.

For urinalysis tests, results will be classified as normal or abnormal. Results out of range will be identified as such on subject listings. Shift tables for urinalysis results using categories of normal and abnormal, comparing laboratory test results from Baseline to each visit will be presented with percentages based on subjects with a non-missing value at Baseline and post-baseline visit.

A listing of urine pregnancy test results will be produced.

In addition, a by-subject listing for laboratory test results will be provided by subject ID number, and time point in chronological order for hematology, serum chemistry, lipids and coagulation, and urinalysis separately. Values falling outside of the relevant reference range and/or having a severity grade of 1 or higher based on the toxicity severity grade will be flagged in the data listings, as appropriate.

No formal statistical testing is planned.

Shift plots may be produced for selected laboratory values.

Laboratory results will be evaluated from Trail and HZN-825 Baselines to the end of HZNP-HZN-825-302 separately as needed.

#### **10.3.3.2 Summaries Liver Function Tests**

Liver-related abnormalities after initial trial drug dosing will be examined and summarized by treatment group using the number and percentage of subjects who were reported to have the following laboratory test values for postbaseline measurements:

- Aspartate aminotransferase (AST):
  - (a) > 3 times of the upper limit of reference range (ULN);
  - (b) > 5 x ULN
  - (c) > 8 x ULN;
  - (d) > 20 x ULN
- Alanine aminotransferase (ALT):
  - (a) > 3 x ULN;
  - (b) > 5 x ULN
  - (d) > 8 x ULN;
  - (e) > 20 x ULN
- AST or ALT:
  - (a) > 3 x ULN;

- (b)  $> 5 \times \text{ULN}$
- Total bilirubin:
  - (a)  $> 1.5 \times \text{ULN}$ ;
  - (b)  $> 2 \times \text{ULN}$
  - (c)  $> 3 \times \text{ULN}$
- Alkaline phosphatase (ALP):
  - (a)  $> 1.5 \times \text{ULN}$ ;
  - (b)  $> 2 \times \text{ULN}$
  - (c)  $> 3 \times \text{ULN}$
- Gamma Glutamyl Transferase (GGT):
  - (a)  $> 2.5 \times \text{ULN}$ ;
  - (b)  $> 5 \times \text{ULN}$
  - (c)  $> 20 \times \text{ULN}$
- Potential Hy's Law: AST or ALT  $> 3 \times \text{ULN}$  and total bilirubin  $> 2 \times \text{ULN}$

The summary will include data from all postbaseline visits up to 28 days after the last dose of trial drug.

For individual laboratory tests, subjects will be counted once based on the most severe postbaseline values. For both the composite endpoint of AST or ALT and total bilirubin, subjects will be counted once when the criteria are met at the same postbaseline visit date. The denominator is the number of subjects in the Safety Analysis Set who have non-missing postbaseline values of all relevant tests at the same postbaseline visit date.

A listing of subjects who met at least 1 of the above criteria will be provided.

Evaluation of Drug-Induced Serious Hepatotoxicity (eDISH) plots will be produced.

Liver function data will be evaluated from Trail and HZN-825 Baselines to the end of HZNP-HZN-825-302 separately as needed.

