**Duration of Treatment and Follow-up:**

The duration of the Treatment Period is 52 weeks. Subjects will participate in a Safety Follow-up Visit 4 weeks after the last dose of fipaxalparant (HZN-825).

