SSPRO-18 (last week)	X 					X				X	
SSPRO-18 (change since start of trial)						X				X	
Pregnancy test 											
Physical examination 	X 					X				X	X
Vital signs 	X 	X	X	X	X	X	X	X	X	X	X
12-lead electrocardiogram 	X 	X		X		X				X	
Echocardiogram 	X										
Clinical laboratory safety tests 											
Chemistry	X 	X	X	X	X	X		X		X	X
Lipids	X 					X				X	
Hematology	X 	X	X	X	X	X		X		X	X
Urinalysis	X 	X	X	X	X	X		X		X	X
ESR  and hsCRP	X 									X	X
Autoantibodies 	X 									X	
PK samples 	X 	X		X		X		X			

Trial Visit	Open-label Treatment Period (Fipaxalparant [HZN-825] 300 mg BID)										Safety Follow-up Visit
	1	2	3	4	5	6	7	8	9	10	
Trial Week (W)	Day 1 	W4	W10 	W16	W22 	W28	W34 	W40	W46 	W52/PD	
Visit Window (±days)		(±5)	(±7)	(±7)	(±7)	(±7)	(±7)	(±7)	(±7)	(±7)	(±14)
Serum biomarkers 											
Plasma biomarkers 											
Adverse event assessment 	X	X	X	X	X	X	X	X	X	X	
Prior/concomitant medications 	X 	X	X	X	X	X	X	X	X	X	

ACR-CRISS=American College of Rheumatology-Composite Response Index in Systemic Sclerosis; BID=twice daily; CGA=Clinician Global Assessment; DLCO=diffusing capacity of the lungs for carbon monoxide; ESR=erythrocyte sedimentation rate; FACIT-F=Functional Assessment of Chronic Illness Therapy – Fatigue Scale; FVC=forced vital capacity; HAQ-DI=Health Assessment Questionnaire – Disability Index; HRCT=high-resolution computed tomography; hsCRP=high-sensitivity C-reactive protein; mRSS=modified Rodnan skin score; PD=premature discontinuation; PK=pharmacokinetic; PTGA=Patient Global Assessment; SF-12=SF-12® Health Survey; SHAQ=Scleroderma Health Assessment Questionnaire; SScQoL=Systemic Sclerosis Quality of Life Questionnaire; SSPRO-18=scleroderma skin patient-reported outcome; UCLA SCTC GIT 2.0=University of California Los Angeles Scleroderma Clinical Trial Consortium Gastrointestinal Tract; W=Week; WOCBP=women of childbearing potential

1. Visits may be conducted as home health visits, as available within local regions.

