### 7.1.3.5 Benefit/Risk Assessment

Fipaxalparant (HZN-825) is a new therapeutic agent under development for treating fibrotic diseases, including SSc. The anti-inflammatory and anti-fibrotic properties of LPAR1 antagonism have been demonstrated in both animal models and in a Phase 2 clinical trial. Positive changes in mRSS, HAQ-DI and LPAR1 pathway genes were detected in the completed Phase 2a trial in diffuse cutaneous SSc. Results of trials to date support the safety and potential efficacy of 300 mg BID for up to 24 weeks of treatment. The exposure, PK and safety profiles of fipaxalparant (HZN-825) were similar across the completed trials.

Based on the cumulative safety data available to date on fipaxalparant (HZN-825), transaminase increase has been evaluated as an important identified risk and [REDACTED], drug-drug interactions, and embryo-fetal toxicity are considered as important potential risks. No severe AEs or SAEs were reported in healthy subjects in Phase 1 trials. TEAEs of [REDACTED] [REDACTED], postural dizziness, flatulence and abdominal pain were slightly more frequent in fipaxalparant (HZN-825)-treated than in placebo-treated subjects. [REDACTED] was mainly observed in healthy subjects and tended to be less marked in subjects with diffuse cutaneous SSc treated with fipaxalparant (HZN-825). The potential safety risk of fipaxalparant

(HZN-825) due to drug-drug interactions is considered low as medications that may have potential interactions with fipaxalparant (HZN-825) are restricted in this protocol (Section 9.4.9).

AESIs are considered monitorable. Taking into account mitigation measures to minimize risk to subjects in this trial, the potential risk identified in association with fipaxalparant (HZN-825) treatment and the trial as a whole are justified by the anticipated benefits that may be afforded to subjects.

More detailed information on the benefits and risks of fipaxalparant (HZN-825) is provided in the Investigator's Brochure Section 6.2 and Section 12.

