### **9.5.3.8 Laboratory Tests for Evaluation**

A central trial laboratory will be used for all protocol-specified laboratory evaluations, with the exception of urine pregnancy tests that will be performed locally at each site or at-home, as applicable, in order to maintain monthly pregnancy testing.

Chemistry parameters to be evaluated include total protein, albumin, sodium, glucose, phosphate, potassium, calcium, chloride, bicarbonate, blood urea nitrogen, creatinine, creatine kinase, uric acid, lactate dehydrogenase and liver function tests (ALT, AST, gamma glutamyltransferase, alkaline phosphatase, total bile acid, TBL, conjugated and unconjugated bilirubin, if applicable).

Lipid profile (total cholesterol, high-density lipoprotein cholesterol, low-density lipoprotein cholesterol, triglycerides) will also be evaluated.

Subjects should be fasting for the Day 1, Week 28 and Week 52/Premature Discontinuation Visits.

Hematology parameters to be evaluated include hemoglobin, hematocrit, red blood cell count (with morphology if blood cell count is abnormal), mean corpuscular volume (MCV), mean corpuscular hemoglobin (MCH), mean corpuscular hemoglobin concentration (MCHC), red blood cell distribution width (RDW), reticulocyte count, white blood cell count with differential (neutrophils, eosinophils, basophils, monocytes, lymphocytes) and platelet count.

Urinalysis parameters, including reflex testing if abnormal on dipstick, to be evaluated include urine glucose, protein, bilirubin, urobilinogen, pH, blood, ketone, nitrite, leukocyte esterase, appearance, specific gravity and color.

Samples for high-sensitivity C-reactive protein (hsCRP), erythrocyte sedimentation rate (ESR) and autoantibodies (anti-centromere antibody, anti-RNA polymerase antibody, anti-topoisomerase 1 and anti-U1 small nuclear ribonucleoprotein) will also be collected.

Instructions for the collection, handling and analysis of clinical laboratory samples will be provided to the site prior to trial site initiation.

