## **4.2 Study Treatments**

The dose regimen for all subjects will be HZN-825 300 mg twice every day for 52 weeks. Subjects will take 2 HZN-825 150 mg tablets orally in the morning and evening with a meal. Subjects will participate in a Safety Follow-up Visit 4 weeks after the last dose of HZN-825.

The treatment group will be based on randomized treatment in previous HZNP-HZN-825-301 trial and denoted as QD/BID (HZN-825 300mg QD/HZN-825 300mg BID), BID/BID (HZN-825 300mg BID/HZN-825 300mg BID), and PLC/BID (Placebo/HZN-825 300mg BID) accordingly.

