## 14 Appendix, Schedule of Assessments (Clinical Study Protocol v2.2)

Trial Visit	Open-label Treatment Period (HZN-825 300 mg BID)										Safety Follow-up Visit   11 4 weeks after last dose of HZN-825
	1	2	3	4	5	6	7	8	9	10	
Trial Week (W)	Day 1 	W4	W10 	W16	W22 	W28	W34 	W40	W46 	W52/PD 	
Visit Window (±days)		(±3)	(±5)	(±5)	(±5)	(±5)	(±5)	(±5)	(±5)	(±5)	(±14)
Informed consent	X										
Review eligibility criteria	X										
Weight	X 					X				X	
HZN-825 dispensing	X	X	X	X	X	X	X	X	X		
Compliance		X	X	X	X	X	X	X	X	X	
mRSS 	X 			X		X		X		X	
FVC % predicted/spirometry 	X 			X		X		X		X	
MDGA	X 			X		X		X		X	
Lung HRCT	X 								X 		
DLCO 	X 					X 			X 		
Patient-reported outcome assessments											
SHAQ	X 			X		X		X		X	
PTGA	X 			X		X		X		X	
UCLA SCTC GIT 2.0	X 					X				X	
SSPRO-18	X 					X		X		X	

Trial Visit	Open-label Treatment Period (HZN-825 300 mg BID)										Safety Follow-up Visit 
	1	2	3	4	5	6	7	8	9	10	
Trial Week (W)	Day 1 	W4	W10 	W16	W22 	W28	W34 	W40	W46 	W52/PD 	
Visit Window (±days)		(±3)	(±5)	(±5)	(±5)	(±5)	(±5)	(±5)	(±5)	(±5)	(±14)
SScQoL	X 					X				X	
SF-12	X 					X				X	
Pain questionnaire	X 					X				X	
Fatigue (FACIT-F)	X 					X				X	
Raynaud's assessment 	X 				X				X		
Anchor questions											
ACR-CRISS (last week)	X 			X		X		X		X	
ACR-CRISS (overall health and change since start of trial)						X				X	
FVC (last week)	X 			X		X		X		X	
FVC (change since start of trial)						X				X	
HAQ-DI (last week)	X 			X		X		X		X	
HAQ-DI (change since start of trial)						X				X	
SSPRO-18 ( last week)	X 					X		X		X	
SSPRO-18 (change since start of trial)						X				X	

Trial Visit	Open-label Treatment Period (HZN-825 300 mg BID)										Safety Follow-up Visit 
	1	2	3	4	5	6	7	8	9	10	
Trial Week (W)	Day 1 	W4	W10 	W16	W22 	W28	W34 	W40	W46 	W52/PD 	
Visit Window (±days)		(±3)	(±5)	(±5)	(±5)	(±5)	(±5)	(±5)	(±5)	(±5)	(±14)
Pregnancy test 											

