Physical examination 	X 					X				X	X
Vital signs 	X 	X	X	X	X	X	X	X	X	X	X
12-lead electrocardiogram 	X 	X		X		X				X	
Echocardiogram 	X										
Clinical laboratory safety tests 											
Chemistry	X 	X	X	X	X	X		X		X	X
Lipids	X 					X				X	
Hematology	X 	X	X	X	X	X		X		X	X
Urinalysis	X 	X	X	X	X	X		X		X	X
ESR  and hsCRP	X 									X	X
Autoantibodies 	X 									X	
PK samples 	X 	X		X		X		X			
Serum Biomarkers 											
Plasma Biomarkers 											
Adverse event assessment 	X	X	X	X	X	X	X	X	X	X	X
Prior/concomitant medications 	X 	X	X	X	X	X	X	X	X	X	X

ACR-CRISS=American College of Rheumatology-Composite Response Index in Systemic Sclerosis; BID=twice daily; DLCO=diffusing capacity of the lungs for carbon monoxide; ESR=erythrocyte sedimentation rate; FACIT-F=Functional Assessment of Chronic Illness Therapy – Fatigue Scale FVC=forced vital capacity; HAQ-DI=Health Assessment Questionnaire – Disability Index; HRCT=high resolution computed tomography; hsCRP=high-sensitivity C-reactive

protein; MDGA=Physician Global Assessment; mRSS=modified Rodnan skin score; PD=premature discontinuation; PK=pharmacokinetic; PTGA=Patient Global Assessment; QD=once daily; SARS-CoV-2=severe acute respiratory syndrome coronavirus 2; SCR=Screening; SF-12=SF-12® Health Survey; SHAQ=Scleroderma Health Assessment Questionnaire; SLCO=solute carrier organic anion transporter family member; SSc=systemic sclerosis; SScQoL=Systemic Sclerosis Quality of Life Questionnaire; UCLA SCTC GIT 2.0=University of California Los Angeles Scleroderma Clinical Trial Consortium Gastrointestinal Tract; SSPRO=scleroderma skin patient-reported outcome; VAS=visual analog scale; W=Week; WOCBP=women of childbearing potential

1. Visits may be conducted as home health visits, as available within local regions.
2. On Day 1 (Baseline), subjects will receive the first dose of HZN-825 in this extension trial in the clinic. All Day 1 assessments should be performed before the first dose of trial drug is administered in the clinic.
3. Performed as part of the Week 52 Visit of HZNP-HZN-825-301; if applicable, the result will be considered a Trial Baseline value for this extension trial.

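### The SAP's 28-day cut on the liver threshold and potential Hy's law counts falls in the middle of the Safety Follow-up window (Days 14 to 42), so read by date it leaves out compliant samples from Days 29 to 42

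*SAP*

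**What the plan says.** SAP 10.3.3.2 plans counts of subjects above set multiples of ULN for AST, ALT, total bilirubin, ALP and GGT. It adds potential Hy's law: AST or ALT above 3 x ULN with total bilirubin above 2 x ULN on the same visit date. It then sets the period: "The summary will include data from all postbaseline visits up to 28 days after the last dose of trial drug". The section closes differently: liver data are to be evaluated from each of the two baselines to the end of the extension trial, separately and as needed.

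The visit in question is fixed in SAP 4.2: "Subjects will participate in a Safety Follow-up Visit 4 weeks after the last dose of HZN-825". The schedule in SAP Appendix 14 heads its last column "4 weeks after last dose of HZN-825" and gives it a window of plus or minus 14 days. The "Safety Follow-up Visit" column in Protocol 2.1 carries the same window. The two schedules differ on the on-treatment visit windows but agree on this one.

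Chemistry is drawn at that visit. The SAP row reads "Chemistry X 3 X X X X X X X X": the empty cells are Weeks 34 and 46, and the last mark is the Safety Follow-up column. Protocol 9.5.3.8 places ALT, AST and total bilirubin in the chemistry panel.

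On the importance of these tests, Protocol 7.1.3.5 states that "transaminase increase has been evaluated as an important identified risk".

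**The concern.** For a subject who takes drug to Week 52, the Safety Follow-up chemistry is the only scheduled liver sample after treatment. The cut falls on that visit's target day, so whether the sample enters the table depends on the calendar day of a visit that is compliant either way. A sample on Day 28 counts and one on Day 29 does not.

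Any error runs in one direction. Leaving out a sample cannot add a subject to a count; it can only remove one. The thresholds affected (3, 5 and 8 x ULN, and 3 x ULN with bilirubin above 2 x ULN) overlap those in the protocol's own liver criteria in 9.3.3.1.

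The text also supports two readings. One programmer could apply the 28-day sentence by date, and another could follow the closing sentence to the end of the extension. They would produce different tables from the same SAP section.

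**Working it through.** **Inputs**
- Cut: 28 days after the last dose (SAP 10.3.3.2).
- Target day of the Safety Follow-up Visit: 4 weeks after the last dose (SAP 4.2; both schedules).
- Window: plus or minus 14 days (Protocol 2.1; SAP Appendix 14).
- Postbaseline chemistry before that visit: Weeks 4, 10, 16, 22, 28, 40 and 52, which is 7 samples (both schedules).

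**The plan's own figures**
- 4 x 7 = 28, so the target day and the cut coincide.
- SAP 10.3.1 uses 392 days, and 52 x 7 + 28 = 392. The same 28-day tail is used there.

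**Days excluded**
- First permitted day: 28 - 14 = 14. Last permitted day: 28 + 14 = 42.
- Permitted days: 42 - 14 + 1 = 29.
- Permitted days after the cut: 42 - 28 = 14 (Days 29 to 42).
- Share of permitted days after the cut: 14/29 = 48.3%. With a limit of Day 42 it would be 0/29.

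**From days to samples (assumption only)**

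The documents give no distribution of visit timing. Give each day d from 14 to 42 a weight exp(-(d - m)²/(2s²)), where m is the typical visit day and s the spread, and take the share of weight on days after 28.

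| m | s | Share after Day 28 |
|---|---|---|
| 28 | 2 | 40.0% |
| 28 | 5 | 46.0% |
| 28 | 10 | 47.7% |
| 21 | 5 | 7.1% |
| 35 | 5 | 89.7% |

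The share of samples could therefore lie almost anywhere, depending on whether visits tend to run early or late.

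**From samples to counts**

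Each subject is counted once, on the most severe postbaseline value (for the combined liver criterion, on values from the same date). A late sample changes a count only if it crosses a threshold that none of up to 7 earlier scheduled samples crossed. The denominator should hardly move, because nearly all subjects will have an earlier postbaseline value. Nothing in the documents allows the number of such subjects to be estimated.

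**Subjects who stop drug early**

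They are asked to stay through Week 52 (Protocol 9.1 and 9.3.3). Take a last dose on the Week 16 visit day and later visits on their target days. Chemistry at Weeks 22, 28, 40 and 52 then falls 6 x 7 = 42, 12 x 7 = 84, 24 x 7 = 168 and 36 x 7 = 252 days after the last dose. The 28-day rule excludes all four samples. A 42-day limit would still exclude three.

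**The case against.** The strongest defence is that 28 days is a deliberate on-treatment period. The primary safety objective runs from Day 1 to 4 weeks after the last dose. Protocol 9.5.3.1.2 ends TEAE reporting at 4 weeks, and SAP 10.3.1 ends TEAEs at 28 days. A liver table on the same period is coherent, and moving it alone would give it a different period from the TEAE tables. This stands as a reason for keeping a 28-day table. It does not explain why one scheduled visit is split by calendar day without saying so, and the 28-day period is not uniform in the documents: schedule footnote 17, in both of them, carries TEAEs through the Safety Follow-up Visit.

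Second, the closing sentence of 10.3.3.2 reaches the Safety Follow-up Visit, since Protocol 9.5.5 ends the trial at the last subject's last visit. That is fair, but the sentence applies only as needed and does not withdraw the 28-day limit. The two sentences need reconciling.

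Third, the late values remain visible. The by-visit summaries, shift tables and flagged by-subject listing in SAP 10.3.3.1 state no cut. No cut is stated for the eDISH plots or for the listing of subjects who meet a liver criterion. Appendix 17.15 asks that confirmed elevations be considered for recording as AEs. All of this stands and limits the point to the count tables. The AE summaries are only a partial backstop: SAP 10.3.1 defines follow-up AEs (more than 28 days after stopping) only for subjects who stop before 52 weeks, so an event starting on Days 29 to 42 in a completer is neither a TEAE nor a follow-up AE as defined there.

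Fourth, if the limit is applied by nominal visit, the 4-week visit is kept. SAP 7.4 leaves window details to the TFL shells, so this reading is open but not stated.

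**Conclusion.** The point holds in a limited form. Read by date, SAP 10.3.3.2 excludes compliant Safety Follow-up samples on 14 of the 29 permitted days from the threshold and potential Hy's law counts, and the exclusion can only lower those counts. The rule does not fit the section's own closing sentence or schedule footnote 17.

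A reader might infer that about half of the follow-up liver samples, or half of the late liver cases, are lost. The documents do not support that. The 48.3% is a share of calendar days. The share of samples depends on visit timing that is not given, and the number of subjects whose count changes is unknown and probably small, because the first crossing would have to occur 29 to 42 days off drug after up to 7 earlier samples. Nor do the documents show that such values disappear from the report or that the eDISH plots and criteria listing are truncated.

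The conclusion assumes that the cut is applied to sample dates. If it is applied by nominal visit, the visit is retained and the remaining defect is that the SAP does not say so. These are descriptive tables with no formal testing, so this is an inexpensive correction to make before the tables are programmed.

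**What to change.** Either of two changes to SAP 10.3.3.2 would do.

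1. Smaller change: let the threshold and potential Hy's law counts take in postbaseline data through the scheduled Safety Follow-up Visit, on whatever day in its window that visit occurs (up to 42 days after the last dose). Flag values first abnormal more than 28 days after the last dose.
2. Fuller change: keep the 28-day table, label it as on-treatment, and add a second table using all data to the end of study. This also covers subjects who stop drug early and stay in the trial, whose later chemistry a 42-day limit would still miss.

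In either case, reword the closing sentence to match and state the same rule for the listing of subjects meeting a criterion and for the eDISH plots.

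The first option costs one sentence and one date parameter in the programs; the second adds a table. The downside is that a few off-drug elevations will be counted and the period will differ from that of the SAP's 28-day TEAE tables. The flag (first option) or the separate on-treatment table (second option) shows which values these are. The change concerns analysis only and alters nothing in how subjects are managed.
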